### 3.5.3 Study Medication

In Phase 1, oral Rifamate will be supplied by the AVRC pharmacy. All medications will be over-encapsulated by the AVRC pharmacist. PDH will supply the ingestible sensor and the AVRC pharmacist will over-encapsulate Rifamate with the ingestible sensor (or in Phase I, the ingestible sensor alone) using an appropriate size capsule, manufactured by Capsugel Inc., according to Standard Operating Procedures. Thus the AVRC will dispense over-encapsulated IS-RM or

Rifamate with co-ingestion of an encapsulated edible sensor to all Phase 1 subjects.

In Phase 2, subjects in the intervention arm will be dispensed study drug, IS-RM, following the process described above, by the AVRC pharmacy to coincide with AVRC visits or study visits with AVRC personnel in Orange County. Control subjects will have medications per SOC prescribed by PHS or OCHCA and dispensed by a public health pharmacy for two, three, or five times a week DOT.

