### 5.2.1 Regimens

DHFS Group:

Rifamate (combination of isoniazid 150 mg and rifampin 300 mg) over-encapsulated with ingestion sensor - 2 capsules orally QD (provided by the study through the AVRC pharmacy)

SOC Control Group:

isoniazid 300 mg -1 tablet orally QD plus rifampin 300 mg - 2 capsules orally QD, or Rifamate (combination of isoniazid 150 mg and rifampin 300 mg) - 2 capsules orally QD (provided by the PHS, OCHCA, or study physician)

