## 9.4 Sample Size and Accrual

Phase 1: For phase 1, both groups will use the DHFS for 2 weeks, and we will estimate the confidence interval around an estimate of the detection accuracy of the DHFS by taking the ratio of the sensor-enabled ingestion recorded events compared to the witnessed doses. Assuming that each of 75 subjects completes 2 weeks of DHFS dosing and has a total of three witnessed doses each week (a total of 450 dosing events) and that the overall rate of positive detection is 95%, then the 95% confidence interval around the point estimate of 95% accurate detection would be  $\pm 2.0\%$ . If the detection accuracy was 97%, then the 95% confidence interval around the point estimate of 97% accurate detection would be  $\pm 1.6\%$ .

Phase 2: The primary aim of phase 2 is to assess the percentage of prescribed witnessed doses completed over the entire study period for each subject and to compare the DHFS arm to the DOT arm. This metric captures the persistent efficacy of the DHFS ingestion sensor system and allows comparison to SOC DOT of varying intervals (5 times, 3 times, or 2 times per week that may occur in the SOC). Sample size calculations were based on a two-sided, two-sample t-test to compare the differences in adherence percentages by treatment arm using different mean/standard deviation scenarios. Calculations were performed using the R statistical package (version 2.14.0) ([www.r-project.org](http://www.r-project.org)).

In choosing a sample size for this pilot study, we considered issues of cost, feasibility, as well as how large an effect size would be of interest to spur further study of this intervention in this population. Assuming a two-sided alpha of 0.05, an adherence percentage in the DOT arm of 90%, and a common standard deviation of 6%, we will need 75 participants (50 DHFS arm and 25 DOT arm) to detect a 5% difference (i.e. 95% adherence percentage in DHFS arm) with 92% power.

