#### Phase 2 (Percentage of Witnessed Doses)

A mixed effects regression model will be used to determine if the WOT intervention arm will produce greater percentage of witnessed doses compared to the DOT standard of care arm at treatment end. This model will include time, treatment arm, and time-by-treatment arm interaction terms. In addition, any covariates, which are simultaneously unbalanced at baseline and associated with the outcome, will be included in the model. Time will be treated as a categorical variable. A significant treatment effect will be concluded if the p-value for the time-by-treatment interaction contrast in the model is  $\leq 0.05$ . Permutation tests may be implemented to verify that valid p-values will be obtained even if model assumptions are not correct. Note that the linear mixed model seamlessly accommodates different times of measurement as well as missed measurements and data from subjects who are lost to follow-up. Generalized estimating equation (GEE) models will be used as the sensitivity analysis method.

Note that when considering percentages of witnessed doses over the entire study period in aggregate, this model reduces to a multiple linear regression, and the independent variable of interest is the treatment arm.

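### The Phase 2 model defaults to one residual variance under 2:1 allocation with dose counts that can differ by arm, so its false-positive rate can move away from 5% (to about 6–8.5% in plausible cases), and the permutation check as written need not correct this

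*Combined protocol and SAP*

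**What the plan says.** - **Sizing (9.4).** "Sample size calculations were based on a two-sided, two-sample t-test to compare the differences in adherence percentages by treatment arm". The inputs are: "Assuming a two-sided alpha of 0.05, an adherence percentage in the DOT arm of 90%, and a common standard deviation of 6" per cent. On these, "we will need 75 participants (50 DHFS arm and 25 DOT arm) to detect a 5% difference"; the power is put at 92%, for a DHFS mean of 95%.
- **Analysis (9.6.1, Phase 2).** A mixed model with time, arm and their interaction, and a decision at p ≤ 0.05 on the interaction contrast. For the whole-study percentage, the section says that the model becomes a multiple linear regression on arm. It mentions neither arm-specific variances nor weighting by number of doses.
- **Safeguards (9.6.1).** "Permutation tests may be implemented to verify that valid p-values will be obtained even if model assumptions are not correct". The use is optional and no statistic is named. GEE is the sensitivity analysis, with no variance estimator named.
- **Dose denominators.** Section 5.2.1 gives DHFS as "2 capsules orally QD (provided by the study through the AVRC pharmacy"). Section 3.5.3 has control medication "dispensed by a public health pharmacy for two, three, or five times a week DOT", and 3.5.2 lists the same three frequencies. Section 5.2.1 also lists the control regimen as QD. The mix of DOT schedules is not given.
- **Precedence (9.6).** A SAP, to be finalised before database lock, overrides this section. No separate SAP text is in the document supplied.

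**The concern.** A percentage built on fewer doses has more sampling variance. If DOT subjects have fewer prescribed witnessed doses than DHFS subjects, and the arms are otherwise alike, the DOT arm is the more variable one. It is also half the size. A single pooled residual variance is then dominated by the larger, less variable arm, and the standard error of the difference is too small.

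The permutation sentence reads as cover for this kind of failure. It is cover only if the statistic is suitable. Shuffling labels and recomputing a raw mean difference mixes the two variances much as pooling does. Unequal dose counts also make the arms non-exchangeable even when their means are equal.

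At stake is whether p ≤ 0.05 in the trial's main randomised comparison means what it says.

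**Working it through.** **1. The plan's power.** SE = 6 × √(1/50 + 1/25) = 6 × 0.2449 = 1.470. The noncentrality is 5 / 1.470 = 3.40 on 73 df, so two-sided power is 91.9%. The stated 92% is reproduced, under equal SDs.

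**2. How dose counts feed the SD.** Let p be mean adherence, τ the between-subject SD and n the number of prescribed doses. If doses are independent within a subject, Var = τ² + (p(1 − p) − τ²)/n. Take p = 0.90 (9.4), τ = 5 points (assumed) and 4 weeks, the Phase 2 minimum in 3.5:

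| Schedule | n | SD | Ratio to DHFS |
|---|---|---|---|
| DHFS, 7 per week (assumed from QD) | 28 | √(0.0025 + 0.0875/28) = 7.5% | 1 |
| DOT, 5 per week | 20 | 8.3% | 1.11 |
| DOT, 3 per week | 12 | 9.9% | 1.32 |
| DOT, 2 per week | 8 | 11.6% | 1.55 |

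**3. What a given SD ratio does to the pooled test.** At a ratio of 1.5 (DHFS variance 1, DOT 2.25), the expected pooled variance is (49 + 24 × 2.25)/73 = 1.411. The pooled SE² is 1.411 × 0.06 = 0.0847, against a true value of 1/50 + 2.25/25 = 0.110. The pooled SE is √(0.0847/0.110) = 88% of what it should be. Simulated false-positive rates (normal data, 50 v 25, equal means, 100,000 trials each):

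| SD ratio DOT/DHFS | Pooled | Welch |
|---|---|---|
| 0.67 | 2.6% | 4.9% |
| 0.8 | 3.5% | 4.9% |
| 1.0 | 4.9% | 5.0% |
| 1.2 | 6.5% | 5.0% |
| 1.4 | 7.8% | 5.0% |
| 1.5 | 8.7% | 5.2% |
| 1.6 | 9.2% | 5.0% |

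**4. Dose-level simulation.** Beta-binomial doses, both arms at 90%, the same τ in each arm, 40,000 trials per scenario. For the single-schedule rows τ is 3 to 6 points and follow-up 4 to 24 weeks. For the equal-mix rows τ is 2 to 6 points, with follow-up varying over 4–12 or 4–24 weeks.

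| DHFS per week | DOT per week | SD ratio | Pooled |
|---|---|---|---|
| 7 | 2 for all | 1.15–1.72 | 6.0–10.2% |
| 7 | 3 for all | 1.08–1.43 | 5.6–8.0% |
| 7 | 5 for all | 1.02–1.15 | 5.0–6.0% |
| 7 | equal mix of 2, 3, 5 | 1.16–1.47 | about 6–8.5% |
| 5 | equal mix of 2, 3, 5 | above 1 | about 5.7–6.8% |
| 5 | 5 for all | 1.0 | about 5% |

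The 10.2% is a corner case: every DOT subject on two doses a week for only 4 weeks, with τ = 3. In the equal-mix row with daily DHFS, the rate is about 6% at τ = 6. Welch gave 4.9–5.7% in the single-schedule runs.

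**5. If the DHFS arm is more variable.** Daily DHFS against the equal mix, 4–24 weeks: τ of 7 v 5 points (DHFS v DOT) gives 4.5%, 6 v 4 gives 4.7% and 8 v 5 gives 3.8%.

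**6. The safeguards.** For normal data at ratios 1.2, 1.4 and 1.5, permuting the raw mean difference gave 7.0%, 8.1% and 8.9%. Permuting the Welch statistic gave 5.6%, 5.4% and 5.2% (Monte Carlo error about 0.4 to 0.6 points). A robust-variance z-test, as in GEE with a sandwich estimator, gave about 6.3–6.5%, against 5.7% at equal SDs.

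**7. Cost of the change.** With equal SDs of 6%, power is 91.4% with Welch and 91.8% with the pooled test (simulated).

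**The case against.** **Direction and size are not in the documents.** No arm-specific SD and no schedule mix are given. Intervention subjects dose without concurrent DOT, and a confirmed dose depends on the patch and system working (3.5.1, 3.6), so the DHFS arm could well have the wider spread. Step 5 shows that a gap of 2 points in τ is enough to remove the inflation. This stands. A reader might infer that the test runs at 6–9% as a matter of fact; the documents do not support that.

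**Missed doses come in runs.** The formula in step 2 treats doses as independent, whereas 9.2.2 anticipates lapses of consecutive doses. With an assumed within-week correlation of 0.2, 0.4 or 0.6, the rate falls to 5.7–6.3%, 5.4–5.8% or 4.9–5.4%. This also stands, and pulls towards the lower end.

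**The decision rule was not simulated.** Section 9.6.1 decides on a time-by-treatment contrast, and the figures here are for the whole-study comparison. The residual structure is unstated, and a SAP could settle it. So the figures describe the default reading, not a demonstrated error rate of the rule.

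**Permutation and GEE may suffice.** A permutation test is exact if the arms have identical distributions, a studentised version holds about 5%, and GEE with robust variance removes most of a large inflation. But identical distributions are what unequal dose counts rule out, neither choice is written down, and GEE is not the primary test.

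**A tempting extra argument fails.** A reader might infer that 90% against 95% contradicts the common SD, since √(0.09/0.0475) = 1.38. That is a ratio of dose-sampling SDs only. The 6% is a total SD that includes between-subject spread, and 90% v 95% is the alternative, so it says nothing about the false-positive rate.

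**Conclusion.** The concern holds as a conditional one. With 50 v 25 subjects, a pooled variance is safe only if the SDs are about equal, and the plan's dose schedules give a specific reason to doubt that.

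If DOT is mostly two or three times weekly, DHFS is daily and between-subject spread is similar, the whole-study comparison could run at about 6–8.5%, and at about 6% with a between-subject SD near 6 points. It stays at about 5–6% with DOT five times weekly, and drops below 5% if the DHFS arm is more variable. These figures rest on an assumed schedule mix, independent doses and the aggregate comparison.

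The permutation test does not correct the error if it permutes the raw mean difference, and the plan leaves that open. Because the error can go either way and the SDs are unknown, the sound course is a method that holds about 5% in both directions.

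**What to change.** - **9.6.1, model.** Prespecify arm-specific residual variances with Satterthwaite degrees of freedom; for the aggregate comparison this is Welch's test.
- **9.6.1, permutation.** State that any permutation test uses the studentised statistic.
- **9.6.1, GEE.** Name the variance estimator. If it is robust, note that with 75 subjects a z-test runs slightly above 5% even at equal SDs.
- **9.4.** State that 92% power assumes SDs of 6% in both arms.
- **5.2.1 against 3.5.2 and 3.5.3.** Reconcile the control regimen given as QD with the two, three or five times weekly schedule, because this sets the DOT denominator.

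The statistical changes are wording only, need no new data and can be made before database lock. The price is about 0.4 points of power (91.8% to 91.4%) if the SDs are in fact equal.

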### 9.6.2 Analysis for Secondary Outcomes

All secondary measures will be summarized descriptively by study arm and overall. Mixed effects regression models analogous to the primary analysis methodology will be applied for the secondary outcomes. There will be no adjustments made for multiple testing corrections for secondary outcomes. P-values less than 0.05 will be considered statistically significant.

The percentage of subjects completing > 80% prescribed witnessed dosing for TB treatment using DHFS and SOC, respectively will be calculated and compared using two sample t-tests (or non-parametric equivalent) for the duration of follow-up. The time to first evidence of < 80% adherence will be calculated in the DHFS only as this may not be available in the SOC data.

The number of lapses in witness doses will be compared between DHFS and SOC using Wilcoxon rank sum test. The longest duration of lapse in witnessed treatment will be calculated and compared between the DHFS and SOC groups.

Data collected and model considerations for the costs analyses will include: 1) number of visits from outreach worker divided by length of time on study, 2) outreach worker hours spent per subject divided by length time on study; 3) distanced traveled per subject divided by length of time on study; 4) distance traveled by outreach worker divided by length of time on study, and 6) number of hospitalizations divided by length of time on study. Patient travel costs and lost wages will be reported. Wage costs with benefits of County workers and time spent per case will be calculated. Sensitivity analyses as appropriate with variation of costs and rates of failure derived from pre-existing County data will be performed of DHFS and DOT and will include all costs related to TB treatment, laboratory monitoring, assessment and treatment of adverse events, costs of DHFS and equipment associated with DHFS.

Adverse events related to study procedures (either DHFS or SOC DOT) will be graded using standard ACTG grading tables and listed by organ system and severity. Of note, GI symptoms, hepatic enzyme abnormalities, or other expected toxicities of Rifamate or TB disease itself that were pre-existing and were not exacerbated during the study will be recorded, but will not be adjudicated as related or possibly related to DHFS.

Subject responses regarding satisfaction with the DHFS and DOT will be reported on post study questionnaires regarding their experience with the DHFS and the usability of the system, using summary statistics. Questionnaire responses by subjects will be examined by study reviewers from AVRC and will present a set of recommendations regarding the usability of the system. Areas evaluated may include ease of use, time needed to use the system, perceived personal benefit, negative impressions, risk of disclosure of health status and changes to quality of life. Analyses of individual questions as well as summary metrics across questions will be explored. Analyses will use descriptive statistics. If there is variation in satisfaction with the DHFS, the demographic characteristics potentially related to different levels of satisfaction will be explored.

Healthcare and physician satisfaction with the DHFS will be reported quantitatively, using non-standard customized questionnaires to collect information regarding their experience with the DHFS and the usability of the system, using summary statistics. Questionnaire responses by providers will be examined by study reviewers from AVRC and make a set of recommendations

regarding the usability of the system. DOT satisfaction will be reported using questionnaires.

Summary statistics will be used to define the results of self-reported instruments. Comparisons between groups will use Fisher's exact test or Wilcoxon rank sum test as appropriate.

Reported clinical and demographic characteristics, as well as responses to self-reported questionnaires, will be compared for subjects with < 80% adherence to those with greater than 80% adherence. Comparisons will include: demographics, disease characteristics, and self-reported metrics. Self-reported metrics will be defined based on the individual instrument. For example, depression will be defined as a PHQ-9 score > 5.

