**Figure 1. AHF TB 001 Study Schema**

## 1.0 HYPOTHESIS AND STUDY OBJECTIVES

### 1.1 Hypotheses

- 1.1.1 Direct confirmation of TB medication dosing by DHFS is feasible for monitoring TB treatment.
- 1.1.2 DHFS can be used as an alternative to SOC DOT for monitoring and documenting completion of TB treatment.
- 1.1.3 The cost of TB target treatment using DHFS is comparable or favorable when compared to DOT for monitoring a comparable number of targeted doses.
- 1.1.4 DHFS is safe for use in TB treatment.
- 1.1.5 Patient satisfaction with DHFS use for TB treatment is rated as ‘satisfactory’ or higher.
- 1.1.6 Healthcare worker and physician satisfaction with DHFS for TB treatment is rated as ‘satisfactory’ or higher.
- 1.1.7 DHFS subjects have similar or better self-efficacy scores than control subjects receiving SOC DOT during and at the end of the trial.

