**Figure 2. AVRC/County Outreach Worker Algorithm Used for Wirelessly Confirmed Ingestions**

Safety laboratory values will be reviewed at Weeks 2, 4, 8, and every 4 weeks until the completion of TB treatment (up to a maximum of 12 months on study) and at the end of study, or at frequency of PHS or OCHCA SOC. For the full schedule of events at these weeks, see Section 6.1.

In Phase 2 on Day 0, Week 8, and at the end of study, subjects will be asked to complete the following questionnaires: habitual self-control, self-efficacy beliefs, depression scale (PHQ-9), alcohol use (AUDIT), and drug use (DAST-10). Questionnaires will be available in English and Spanish; for subjects with other

first languages, questionnaires will be administered with the aid of an interpreter, if necessary. All self-report questionnaires will be completed via a study tablet device. Questionnaires will automatically upload to a secure server after completion.

As indicated above, each intervention subject will also be followed by County healthcare workers, who will collect and follow data on intervention subjects following County routine practice, including data from medical records, adherence data as witnessed ingestions, cost data, any toxicity data and side effect data pertaining to non-DHFS medical treatment, including number of clinic visits and number of hospitalizations related to TB treatment, per patient during the study period. AVRC study staff must ensure that data from County records and medical records are on study CRFs and entered into the study database.

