### 3.5.2 Control Group

Subjects randomized to the control arm will receive SOC DOT with isoniazid plus rifampin, or Rifamate via the County healthcare workers. Safety laboratory values will be reviewed as per County SOC. At Phase 2 Day 0, Week 8, and at subject's termination on the study, the following questionnaires will be administered: habitual self-control, self-efficacy beliefs, depression scale (PHQ-9), alcohol use (AUDIT), and drug use (DAST-10). Questionnaires will be available in English and Spanish; for subjects with other first languages, questionnaires will be administered with the aid of an interpreter, if necessary. These data will be identified by subject's participant number only and will not be associated with the subject's name. All self-report questionnaires will be completed via a study tablet device. Questionnaires will automatically upload to a secure server after completion.

County healthcare workers will collect and follow data on control subjects following County routine practice, including data from medical records, adherence data as prescribed DOT (two, three, or five times per week), actual witnessed ingestions, cost data, any toxicity data and side effect data pertaining to treatment, including number of clinic visits and number of hospitalizations related to TB treatment, per patient during the study period. AVRC study staff must ensure that data from County records and medical records are on study CRFs and entered into the study database.

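### Section 9.6.2 gives two unranked analyses for the self-report scores, and neither prespecifies the baseline score as a covariate

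*Combined protocol and SAP*

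**What the plan says.** The instruments are secondary endpoint 1.2.9. Two parts of Section 9.6.2 apply to them.

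- Near the end of the section, comparisons between groups on the self-reported instruments are assigned to Fisher's "exact test or Wilcoxon rank sum test as appropriate". The text does not give the visit, or say whether the tested quantity is a final score, a change or a category.
- At its start, a general sentence covers every secondary endpoint: "Mixed effects regression models analogous to the primary analysis methodology will be applied for the secondary outcomes".

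Section 9.6.1 defines that primary model. Time is categorical, and "This model will include time, treatment arm, and time-by-treatment arm interaction terms". It adds that "any covariates, which are simultaneously unbalanced at baseline and associated with the outcome, will be included in the model". No threshold is given for imbalance or for association, and no baseline score is named.

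The scores are collected repeatedly in both arms. For the intervention arm, Section 3.5.1 states "In Phase 2 on Day 0, Week 8, and at the end of study, subjects will be asked to complete the following questionnaires". For the control arm, Section 3.5.2 gives the same schedule: "At Phase 2 Day 0, Week 8, and at" termination. Table 1 in Section 6.1 also marks these questionnaires at Phase 1 Day 0, before randomization.

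One of the scales carries a stated hypothesis, 1.1.7: "DHFS subjects have similar or better self-efficacy scores than control subjects receiving SOC DOT during and at the end of the trial".

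**The concern.** A score measured before treatment usually predicts the same score measured later. A between-arm test that ignores it gives up precision, and in a comparison of 50 with 25 subjects a chance gap at baseline carries through in part to follow-up. The tests named for these instruments ignore it. The other analysis named for them might use it, but only through a covariate rule applied after looking at the data, or through an unstated choice to treat Day 0 as a response.

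Two things are at stake. First, with two unranked analyses and an open covariate rule, the result reported for hypothesis 1.1.7 could be chosen after the data are seen. Second, that hypothesis says similar or better. A non-significant rank test cannot show similarity. That needs an estimated difference with a confidence interval, and the interval should be as narrow as the collected data allow.

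**Working it through.** **The plan's own figure.** Section 9.4 states 92% power for the primary endpoint (50 and 25 subjects, difference 5, SD 6, two-sided 0.05). The noncentrality is 5 / (6 × √(1/50 + 1/25)) = 5 / 1.470 = 3.40. With 73 degrees of freedom this gives 91.9%, so the figure reproduces. No power or precision is stated for the questionnaire scores.

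**Inputs.** Arm sizes of 50 and 25 are from Section 9.4. The correlation r between baseline and follow-up score is not in the documents and is assumed at 0.3, 0.5 and 0.7. Scores are taken as normal, with a common SD at both times and complete data.

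**Standard error of an unadjusted comparison.** √(1/50 + 1/25) = √0.06 = 0.245 SD. The 95% half-width is about 1.99 × 0.245 = 0.49 SD. The difference detectable with 80% power is (1.960 + 0.842) × 0.245 = 0.686 SD.

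**Three ways to compare the arms at follow-up.** Relative to a variance of 1 for the unadjusted final score, adjustment by analysis of covariance (ANCOVA) gives 1 − r², and a Day 0-to-end change gives 2(1 − r). ANCOVA therefore saves r² against the final score. Against the change it saves 1 − (1 − r²)/[2(1 − r)] = (1 − r)/2.

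| r | ANCOVA variance | Change variance | Saving vs final score | Saving vs change | ANCOVA detectable difference (SD) | ANCOVA 95% half-width (SD) |
|---|---|---|---|---|---|---|
| 0.3 | 0.91 | 1.40 | 9% | 35% | 0.655 | 0.47 |
| 0.5 | 0.75 | 1.00 | 25% | 25% | 0.594 | 0.42 |
| 0.7 | 0.51 | 0.60 | 49% | 15% | 0.490 | 0.35 |

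The change contrast matters because it is what the mixed model's time-by-arm term estimates if Day 0 enters as a time level. It is more precise than the unadjusted final score only when r exceeds 0.5.

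**Power by simulation.** With 4,000 runs per r, 50 and 25 subjects, and an assumed true difference of 0.5 SD:

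| r | Wilcoxon, final score | Change contrast | ANCOVA |
|---|---|---|---|
| 0.3 | 51% | 40% | 55% |
| 0.5 | 51% | 53% | 64% |
| 0.7 | 51% | 74% | 80% |

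**Chance imbalance.** The baseline difference between arms also has a standard error of 0.245 SD. The probability that it exceeds 0.25 SD in either direction is 2[1 − Φ(0.25/0.245)] = 31%. For 0.5 SD it is 2[1 − Φ(0.5/0.245)] = 4%. A gap of 0.5 SD would shift an unadjusted final-score comparison by r × 0.5, which is 0.15, 0.25 or 0.35 SD at the three values of r.

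**Which baseline.** Table 1 places Phase 2 Day 0 after randomization. The trial is open-label, and Section 6.2.2.1 puts the intervention arm's home-use training in that same visit. A self-efficacy score taken then could already reflect the assignment. The Phase 1 Day 0 score cannot.

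**The case against.** A reader might infer that the plan makes no use of baseline at all and leaves chance imbalance in place. The documents do not support that. The mixed model is also assigned to these outcomes, its covariate rule could bring in a Day 0 score that is unbalanced and prognostic, and a Day 0 time level would absorb part of any imbalance. The primary outcome has no Day 0 value, so the absence of a baseline term in its model says little about the questionnaires. The text is ambiguous on this point. It does not rule adjustment out.

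Other points on that side also carry weight. Objective 1.2.9 is descriptive, the trial is a pilot, and only self-efficacy has a hypothesis. Section 4.2.7 excludes active drug or alcohol use judged likely to interfere with adherence, so AUDIT and DAST-10 may sit near the floor. There a rank test is reasonable, and the normal-theory gains above need not hold. Section 9.6 calls itself brief and defers to the SAP, and the combined document carries no further SAP text on this analysis.

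What remains is that two analyses are unranked, the role of the Day 0 score is unstated, and the only covariate rule depends on the data and has no threshold.

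**Conclusion.** The point holds as one of precision and prespecification in an unpowered secondary analysis. Against an unadjusted final-score comparison, a prespecified baseline covariate would cut variance by 9% to 49%. Against a change contrast it would cut it by 35% to 15%. Both ranges are for r from 0.3 to 0.7. In the simulation ANCOVA had the highest power of the three analyses at each r tried.

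Two stronger readings should be resisted. One is that the between-arm comparison is biased. Randomization keeps the unadjusted test valid on average, and a baseline gap above 0.5 SD has only about a 4% chance. The other is that adjustment is worth 1.3 to 2.0 times the sample. That figure is 1/(1 − r²) at r of 0.5 and 0.7 (1.33 and 1.96), set against the unadjusted final score only. At r = 0.3 it is 1/0.91 = 1.10. The documents give no r for any of the five instruments.

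**What to change.** In the SAP, name one governing analysis for endpoint 1.2.9: ANCOVA, or a mixed model on the Week 8 and end-of-study scores, with arm and a prespecified baseline score as covariate whether or not the arms look balanced. Report the adjusted difference with a 95% confidence interval for each scale, and read hypothesis 1.1.7 from that interval. State in advance what difference in self-efficacy would still count as similar.

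Define baseline as the Phase 1 Day 0 score. Use Phase 2 Day 0 only if the questionnaires are completed before the assignment is disclosed. Section 6.2.1.4 does not mention the Phase 1 Day 0 questionnaires that Table 1 lists, so confirm that they are collected.

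Keep the Wilcoxon and Fisher tests as supportive analyses, stating the visit and the quantity tested. They matter most for AUDIT and DAST-10, which may be skewed.

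The cost is SAP wording. Table 1 already schedules the data, and Section 9.6 has the SAP finalized before database lock.
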